## 2. Weight by beam scale digital scale

**Body Composition:** Lean (fat-free mass) and fat mass will be assessed by:

Bioelectrical Impedance Analysis (BIA) by Tanita scale will be used as a measure of body composition. It provides a measure of % body fat as well as a measure of lean mass.

**Blood Pressure (BP):** BP will be assessed in a seated position after 20 min of rest, using the BPM-200 automated sphygmomanometer (BpTRU Medical Devices, Coquitlam BC, Canada), which meets or exceeds the Advancement of Medical Instrumentation standards for overall accuracy vs. auscultation. BP with this instrument is accurate within 3 mm Hg or 2%, whichever is greater. (Duration: 5 min)

**Fasting Blood Plasma Samples:** Biomarkers will be used to confirm 24-hr dietary recalls of F&V intake. F&V intake has been shown to consistently correlate with carotenoids. Blood samples will be collected from a forearm vein in the Clinical Research Unit (CRU). Plasma carotenoid concentrations are sensitive to small changes and to both high and low F&V intake. Additional plasma samples will be assayed for total cholesterol, LDL, HDL, triglycerides, glucose, HbA1C, protein bound glucose, CRP, electrolytes and liver function by Quest Diagnostics. (Duration of blood draw: 5 min)

## Specimen Collection

**Blood Plasma Samples:** Biomarkers will be used to confirm 24-hr dietary recalls of F&V intake. F&V intake has been shown to consistently correlate with carotenoids. Blood samples will be collected from a forearm vein and kept in EDTA-coated tubes in aluminum foil to protect from light. The samples will be centrifuged at 4°C to obtain plasma and kept in labeled cryomicrotubes at -80°C until assayed. Otherwise they will not be stored further. Carotenoids (lutein, zeaxanthin, alpha-carotene, beta-carotene, beta-cryptoxanthin, trans-lycopene, cis-lycopenes) will be assayed at the Carotenoids and Health Laboratory, USDA-Human Nutrition Research Center on Aging, Tufts Univ. Carotenoids will be measured by high-performance liquid chromatography (HPLC) with a C30 column from plasma that has been extracted with CHCl3:CH3OH (2:1, v/v) and hexane. Age, gender, dietary fat intake, vitamin supplement intake, and BMI will be used as covariates for the analyses.

## Data Management and Confidentiality

Purchasing data will be collected via supermarket scan-card technology by Allegiance and sent to the research team over a secured server. Other data will be collected at assessment visits. Blood samples will be collected and analyzed by the Tufts Carotenoids and Health Laboratory for plasma carotenoids levels. Other blood samples will be analyzed by a commercial laboratory (Quest Lab) for cholesterol (LDL and HDL), glucose, CRP, HbA1C, and triglycerides. Personal information and data will be obtained from questionnaires and clinical interviews, dietary intake records, and psychological scales. These data will be used to evaluate the effectiveness of the interventions. The information will be used for research purposes only, and will be stored in a secure place at the hospital. It will be kept strictly

	Protocol Name:	Multi-level supermarket discounts of fruits and vegetables on intake and health
	Principal Investigator:	[name]
	Primary Contact Name/Contact Info:	[name] [contact] [name] [contact]
	Date Revised:	8/7/20
	Study Number:	HS#: 16-00407 GCO#: 16-1050

confidential, and a person's identity will not be revealed when the data are published. Upon participant request, samples for measurement in the lab will be de-identified using a pseudonym prior to submission to Quest Diagnostics.

All data collected will be kept in strict confidence. No information will be given to anyone without permission from the participant. With participant permission in the informed consent, the participant's PCP may be contacted if the participant lab results are concerning. The PCP will receive a copy of the participant's lab results for further follow-up. We will also send a copy of the signed consent form to Allegiance.

Confidentiality will be assured by use of coded data, whether generated in the supermarket or in the hospital, with a randomly generated code number unique to the participant. The database will be secured with password protection. The data manager will receive only coded information to be entered into the database under those codes. Electronic communication with outside collaborators will involve only coded, unidentifiable information. AE reports and annual summaries will not include subject-identifiable material and will use only coded identification numbers.

Locked file cabinets will be used to store subjects' folders. The study team will review new data for completeness and accuracy, enter the data into a password-protected network database, and double-check the data. Subjects with missing data will be contacted as soon as possible. The data analyst will supervise data management, implement protocols for missing data, and conduct preliminary data analyses.

## Provisions to Monitor the Data to Ensure the Safety of Subjects

### Part I: Elements of a Data and Safety Monitoring Plan

**MSSM Principal Monitor:** [name]

*Indicate whether this person is the PI, a Team Member, or is Independent:* Independent

*Last Name:* [name]

*First Name:* [name]

*Academic Title:* Professor, Division of Endocrinology MSSL

*Department:* Medicine

*Mailing Address:* [name]

*[contact]

*Fax:* N/A

*E-mail:* [name] [contact]

**MSSM Additional Monitor:** N/A

	Protocol Name:	Multi-level supermarket discounts of fruits and vegetables on intake and health
	Principal Investigator:	[name]
	Primary Contact Name/Contact Info:	[name] [contact] [name] [contact]
	Date Revised:	8/7/20
	Study Number:	HS#: 16-00407 GCO#: 16-1050

The safety officer for this trial, [name], is Professor of Medicine in the Division of Endocrinology at MSSL. [name] has experience conducting clinical research studies and has a good understanding of obesity research. She will review the reports sent by the research coordinator at the frequency outlined above and will use the checklist attached to this document to determine whether there is any corrective action, trigger of an ad hoc review or stopping rule that should be communicated to the PI, the hospital IRB, and the NIH. In addition, the safety officer may indicate whether the study investigator should report any specific out-of-range laboratory data to the participants and their physician.

*3. List the specific items that will be monitored for safety (e.g., adverse events, subject compliance with the protocol, drop outs, etc.).*

- Subject accrual, adherence to inclusion/exclusion criteria
- Adverse events
- Participant compliance to treatment protocol

*4. Indicate the frequency at which **ACCUMULATED** safety and data information (items listed in number 3 above and interim analysis of efficacy outcomes) will be reviewed by the monitor(s) or the Data Monitoring Committee (DMC). Although this information must be reviewed at least annually, the higher the study risks, the more frequently reviews must be scheduled.*

**Measurement and reporting of subject accrual, adherence to inclusion/exclusion criteria**

Review of the rate of subject accrual and adherence to inclusion/exclusion criteria will occur bimonthly during the recruitment period. This will assure that participants will meet eligibility criteria and ethnic diversity goals outlined in the grant application.

**Reporting of adverse events**

SAEs that are unanticipated or possibly related to the study intervention will be reported to the Safety Officer and PI as they happen, and to the IRB and NIH within two weeks. Anticipated SAEs or those unrelated to the study intervention will be reported to the Safety Officer and PI as they happen, and to the IRB and NIH on a monthly basis.

An annual report will include a list and summary of adverse events. In addition, the annual report will address:

(1) whether adverse event rates are consistent with pre-study assumptions, (2) reason for dropouts from the study, (3) whether all participants met entry criteria, (4) whether continuation of the study is justified in order to collect additional data to accomplish the aims of the study, and (5) whether conditions are such that the study should be terminated prematurely. The annual report will be signed by the Safety Officer and will be forwarded to the IRB and the NIH. A statement reflecting the results of the review will be sent to the NIH in the annual report (non-

	Protocol Name:	Multi-level supermarket discounts of fruits and vegetables on intake and health
	Principal Investigator:	[name]
	Primary Contact Name/Contact Info:	[name] [contact] [name] [contact]
	Date Revised:	8/7/20
	Study Number:	HS#: 16-00407 GCO#: 16-1050

competing continuation). The adverse event form will be used by the study staff to report adverse events as they happen. The study statistician, the principal investigator, and the safety officer will review adverse event rates bimonthly. Serious adverse events will be reported to the IRB, and the NIH.

*5. Where applicable, describe rules which will guide interruption or alteration of the study design.*

We will monitor adverse effects in all participants; and the safety officer, together with the PI, will alert the IRB and the NIH if a larger than reasonably expected adverse rate should occur. Other issues relating to stopping rules for this trial include:

- **New information**

It is unlikely that new information will become available during this study that would necessitate stopping it

- **Limits of assumptions**

It is possible that excessive study dropouts and/or missing data by interim measurement time points will limit the value of data analysis of measurements. We have allowed for a 37.5% drop out rate, and a rate higher than 47.5% would be of concern. The dropout rate will be monitored semiannually.

- **Limits of rules**

We acknowledge that there are other situations that could occur that might warrant stopping the study, which would be included in "Other situations that have occurred since the last safety report that warrant discussion," to allow for communication of concerns to the study PI, statistician, and the safety officer.

*6. Where applicable, indicate dose selection procedures that will be used to minimize toxicity.*

N/A

*7. List any specialized grading system that will be used to evaluate adverse events (e.g., National Cancer Institute Common Toxicity Criteria).*

**The following definitions will be used to grade adverse events:**

An adverse event (AE) is defined here as any untoward medical occurrence that is temporally associated with participation in the clinical study. An adverse finding can include a sign, symptom, abnormal assessment (laboratory test value, vital signs, electrocardiogram finding, etc.) or any combination of these. A serious adverse event (SAE) is any adverse event that results in one or more of the following outcomes: death, life-threatening event, inpatient hospitalization or prolongation of existing hospitalization, persistent or significant disability/incapacity, congenital anomaly or birth defect, significant medical event based on clinical judgment. AE

 Mount Sinai	Protocol Name:	Multi-level supermarket discounts of fruits and vegetables on intake and health
	Principal Investigator:	[name]
	Primary Contact Name/Contact Info:	[name] [contact] [name] [contact]
	Date Revised:	8/7/20
	Study Number:	HS#: 16-00407 GCO#: 16-1050

severity will be graded by severity (mild, moderate, or severe) depending on the intensity of the event for the participant. An AE will be termed 'mild' if it does not have a major impact on the participant, 'moderate' if it causes the participant some minor inconvenience and 'severe' if it causes a substantial disruption to the participant's well-being. A participant can have a severe event that is not a SAE and a moderate event that meets the SAE definition. AE's will also be categorized according to the likelihood that they are related to the study intervention as: definitely, probably, possibly, or unrelated to the study intervention.

*8. Describe procedures that will be used to assure data accuracy and completeness.*

Purchasing data is automatically saved via scan-card technology: therefore very few, if any, errors should occur. All data collected will be imported to SPSS for analyses and double-checked to minimize data entry errors. Range checks will be applied to all data entered, and out-of-range values will be compared with original data forms.

*9. Should a temporary or permanent suspension of your study occur, in addition to the PPHS, indicate to whom (NIH, FDA, sponsor, IRB) will you report the occurrence.*

**NIH**

**Part II. Data Monitoring Committee/Data Safety Monitoring Board (DMC/DSMB)**

**N/A**

**6) Withdrawal of Subjects**

Data from subjects who show little or no purchasing for 8 weeks will be dropped from the study. Otherwise, no pressure will be exerted on the subjects to participate, and they have the right to withdraw from the study at any time. Once an issue is identified, subjects will be contacted by the research team. If there is not resolution of the issue within the following week, the subject will be removed (dropped) from the study, and their discounted card (when applicable) will be deactivated. Data will be analyzed for participants with complete data sets up through Study Visit 3 (week 24). Participants with fewer data points due to drop-out will not be included in analyses.

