### e) Endpoints

The primary endpoints will be at 40 and 56 weeks of participation. Once participants have started the intervention, data on compliance to the protocol will be collected at each visit by research staff and reviewed quarterly by the PI, the study statistician, and the safety officer. Compliance by participants will be evaluated by reviewing records. Data from subjects who show little or no purchasing during the first 8 weeks will be withdrawn from the study and from the analyses. If any serious issue arises, the study team will contact the individual to try to resolve any problems that exist. If the safety officer has concerns about whether compliance has reached a level that might inhibit the ability of the study to test its primary hypotheses, suggestions will be made for improving compliance.

An annual report will include a list and summary of adverse events. In addition, the annual report will address: (1) whether adverse event rates are consistent with pre-study assumptions, (2) reason for dropouts from the study, (3) whether all participants met entry criteria, (4) whether continuation of the

	Protocol Name:	Multi-level supermarket discounts of fruits and vegetables on intake and health
	Principal Investigator:	[name]
	Primary Contact Name/Contact Info:	[name] [contact] [name] [contact]
	Date Revised:	8/7/20
	Study Number:	HS#: 16-00407 GCO#: 16-1050

study is justified in order to collect additional data to accomplish the aims of the study, and (5) whether conditions are such that the study should be terminated prematurely. The annual report will be signed by the Safety Officer and will be forwarded to the IRB and to the NIH. A statement reflecting the results of the review will be sent to the NIH in the annual report (non-competing continuation). The adverse event form will be used by the study staff to report adverse events as they happen. The study statistician, the principal investigator, and the safety officer will review adverse event rates quarterly. Serious adverse events will be reported to the IRB, and if appropriate to NIH.

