## **f) Procedures Involved in the Human Research**

**Baseline Period:** The 8 week baseline period and preceding pre-baseline period, will give subjects time to adjust to food shopping in one Allegiance affiliated supermarket. We will also monitor protocol compliance and spending level. The average amount spent on food shopping for the home per year per household (average 2.5 persons) for the NYC area is \$4066  $\pm$ 112 SEM [144]. Those not meeting a minimum of \$29/wk (~3 SD from the mean), or not reachable by phone for 24-h recalls, will be withdrawn from the study. 24-hour recalls will be obtained by phone calls in between visits. Under-

	Protocol Name:	Multi-level supermarket discounts of fruits and vegetables on intake and health
	Principal Investigator:	[name]
	Primary Contact Name/Contact Info:	[name] [contact] [name] [contact]
	Date Revised:	8/7/20
	Study Number:	HS#: 16-00407 GCO#: 16-1050

reporting of energy intake is common, and will be checked by comparing dietary recalls with estimated basal metabolic rates, via prediction equations. Deviations of reported energy intake from expected will be used as a covariate (compliance scale, 1-5) in the analyses.

**Intervention Period:** After the 8-wk baseline period, we will continue to monitor subjects' purchasing on a bimonthly basis to ensure that the card is being used. Subjects will be encouraged to contact us with any questions or concerns.

**Follow-up Period:** There will be a confidential exit interview with subjects at the end of the study (wk 56). The interview will follow after the final study payment, if possible, to decrease social desirability bias in responses. The interview will review compliance with the protocol, help detect any previous reporting bias, and obtain feedback about the subjects' experience. (**Appendix H**) (Duration: 10 min)

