#### Study visit 2; wk 8 (Duration ~20 min)

In addition to the general chemistry panel, the blood draw will be used to assess carotenoids to reflect F&V intake (only if the participant is not currently taking vitamin A supplements).

At this study visit, they will be informed of their randomization into 1 of 3 discount level groups, stratified by gender within each grocery store. Subjects will receive, in paper, if they wish, and e-mail format, a summary of foods and beverages available for discount during the study as well as a list of conditions to remain in the study. Subjects will be asked to save their receipts if they believe they did not receive the expected discount, to bring to our attention (rather than to store staff or managers) at their next visit for possible reimbursement.

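### Protocol sections 5e and 6 disagree on whether the low-purchasing exclusion ends with the baseline; applied after week 8, it would drop data on a variable the discount is meant to change

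*Protocol*

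**What the plan says.** The protocol gives the low-purchasing rule twice, with different windows.

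- Section 5e (Endpoints): "Data from subjects who show little or no purchasing during the first 8 weeks will be withdrawn from the study and from the analyses". The first 8 weeks are the baseline, with no discount in force.
- Section 6 (Withdrawal of Subjects): "Data from subjects who show little or no purchasing for 8 weeks will be dropped from the study". No period is named. If an issue is not resolved within a week, "the subject will be removed (dropped) from the study, and their discounted card (when applicable) will be deactivated".

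Section 5f sets the minimum spend of $29 a week under the Baseline Period, next to "We will also monitor protocol compliance and spending level". Its Intervention Period paragraph then says: "After the 8-wk baseline period, we will continue to monitor subjects' purchasing on a bimonthly basis to ensure that the card is being used". That paragraph attaches no withdrawal consequence. Participants learn their arm at the week-8 visit, where "they will be informed of their randomization into 1 of 3 discount level groups".

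Section 6 also restricts analysis to people with full data through the week-24 visit and leaves out those who dropped out sooner. The SAP differs. Its primary analysis is ITT, meaning anyone with one or more measurements after randomisation; it has no purchasing criterion, makes completers a secondary analysis and assumes data are missing at random.

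**The concern.** A purchasing screen confined to the baseline is harmless to the comparison: it acts on behaviour before anyone knows their arm. The same screen used after week 8 acts on behaviour that the discount may have altered. Fruit, vegetable and beverage purchasing is an Aim 1 outcome, and the Economic Analysis paragraph of the Background expects discounts to bring more frequent shopping. Removing people for buying little would then select each arm on its response to the intervention. Even with equal numbers removed, the result would describe only people who kept shopping. With unequal numbers, the arms would no longer be comparable as randomised. Removal also ends collection of intake and weight data that could still have been obtained.

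**Working it through.** **1. Which window applies?**

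- For baseline only: section 5e says so, and the $29 threshold sits under the Baseline Period.
- For later use: section 6 leaves out the limit. Its removal step includes that "their discounted card (when applicable) will be deactivated", and a discounted card can exist only after week 8. Section 5f keeps checking "purchasing on a bimonthly basis to ensure that the card is being used" during the intervention.

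The two sections conflict, and removal after allocation is a fair reading of section 6.

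**2. Does the SAP's ITT set catch these people?** Take someone who stops buying at week 8. Eight weeks without purchases plus one week to resolve: 8 + 8 + 1 = week 17. Store data arrive monthly (section 4), so add about 4 weeks: week 21. Both fall before week 24, the first visit after allocation. Weight, a primary outcome in the SAP, is measured at visits, so this person has no post-randomisation weight. Intake is less clear, because recalls are taken by phone. The Study Visit 1 text puts them in a week between visits, which could fall before removal. The 24-h Dietary Recalls paragraph puts them mid-period; the middle of the 32-week intervention is 8 + 16 = week 24, which is after it.

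**3. Does the missing-at-random assumption cover later removals?** Removal would depend on purchasing. The primary model contains group, time and participant, without covariates, so purchasing is not in it. For intake and weight, the assumption holds only if the earlier values of the same outcome account for the link.

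**4. The plan's own figure.** 360 × (1 − 0.375) = 225 completers, as stated in sections 4 and 5c. (Section 5a's pairing of 20% with 240 does not reproduce: 360 × 0.80 = 288.) Neither figure is split by arm or by reason, so the bias cannot be computed from the documents. The rest is illustration.

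**5. Intake, simple model.** Assumptions: removed people's data are lost entirely; they eat 20% less fruit and vegetables than their arm's mean; the true ratio of the 30% arm to control is 1.15. The last extrapolates the Background figure of 5% more consumption per 10% price cut. If a fraction p is removed, the retained mean relative to the arm mean is (1 − 0.8p)/(1 − p).

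| Removed, control / 30% arm | Retained mean, control | Retained mean, 30% arm | Ratio seen |
|---|---|---|---|
| 5% / 2% | 1.0105 | 1.0041 | 1.15 × 1.0041/1.0105 = 1.143 |
| 10% / 4% | 1.0222 | 1.0083 | 1.15 × 1.0083/1.0222 = 1.134 |
| 15% / 5% | 1.0353 | 1.0105 | 1.15 × 1.0105/1.0353 = 1.122 |

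**6. Any continuous outcome, truncation model.** Assumptions: the lowest purchasers in each arm are removed, and purchasing and outcome are jointly normal with correlation ρ from 0.2 to 0.6. Shift in the discount-minus-control difference = ρ × [m(p, discount) − m(p, control)], in SD units, where m(p) = φ(z_p)/(1 − p). Values: m(0.05) = 0.109, m(0.10) = 0.195, m(0.20) = 0.350.

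- 10% of control and 5% of discount removed: ρ × (−0.086) = −0.02 to −0.05 SD.
- 20% and 5%: ρ × (−0.241) = −0.05 to −0.15 SD.
- Equal removal: 0.
- Rule confined to the baseline: no between-arm bias.

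**The case against.** A reader might infer that section 6 removes people after any 8-week lapse, and that more controls will therefore be lost. The documents support neither as fact. The sentence does not say any 8 weeks, section 5e states the same rule for the first 8, and the card-deactivation step follows a general passage on withdrawal and may serve removals for other reasons.

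On differential loss, no arm-specific rate is given and several features work against it. Controls receive 30% off after week 56, expressly to keep them motivated. Every arm agrees to do all its grocery shopping at the store. Payments, including the completion bonus, are the same. The rule also concerns purchasing in general, while the Background puts fruit and vegetables at about 11% of supermarket sales, so the discount need not decide who shops there. Removals may differ by arm; more cannot be said.

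A reader might also infer that the ITT set gives no protection. It gives a good deal: anyone removed after a first post-randomisation measurement stays in the primary analysis, and a phone recall may provide one. Week 17 is the earliest removal date; a two-monthly check or a delayed data transfer could push it later.

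What stands is the conflict over the window, the loss of post-randomisation weight for anyone removed before week 24, the end of data collection at removal, and section 6's explicit restriction to people with complete data to week 24.

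**Conclusion.** The concern holds as a conflict between sections 5e and 6 that leaves room for exclusion after allocation on a variable the discount is meant to change. The SAP's ITT definition reduces the consequence without removing it. The size is unknown. Under the assumed removal rates, a true intake gain of 15% would be seen as about 12.2 to 14.3%, and the truncation model gives a shift of 0.02 to 0.15 SD. Both run towards no effect if more controls are removed, and the direction would reverse if more discount participants were. These figures assume that removed people's data are lost entirely, so they overstate the effect wherever ITT keeps some of the data. For intake this is a modest bias, not one that would by itself overturn a clear result. The complete-to-week-24 restriction in section 6 contradicts the SAP whichever window is meant.

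**What to change.** - Reconcile sections 5e and 6 so that exclusion of data for low purchasing is confined to the 8-week baseline, before allocation is disclosed, and state the threshold for little purchasing.
- After week 8, record low card use as non-adherence. Continue visits and recalls where the participant agrees, and analyse everyone in the assigned group with observed purchases, zeros included. Whether a card is deactivated is for the study team; it need not end measurement.
- Delete section 6's restriction to people with complete data to week 24, or label that subset secondary, so that it agrees with the SAP.
- Report removals for low purchasing by arm and by week. The SAP is written in the past tense; if data collection has closed, this report and the alignment of analysis sets are what can still be done, since measurements not taken cannot be recovered.

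The cost is a short amendment to section 6, visits and payments for a few non-shoppers, and an effect estimate that includes non-adherers.
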